9.1 Adverse Event Definition

An AE is any untoward medical occurrence in a study subject administered a pharmaceutical product and may not necessarily have a causal relationship with the administered treatment. An AE can therefore be any unfavorable and unintended sign (including a clinically significant laboratory abnormality, for example), symptom, or disease temporally associated with the use of a medicinal (investigational) product, regardless of its relationship to the medicinal (investigational) product. During the study, an AE can also occur outside the time that the study drug(s) was given (e.g., during the time from discontinuation of prohibited medications). Preexisting conditions, diseases, or disorders are not considered AEs unless there is a change in severity, frequency, or quality.

9.2 Serious Adverse Events and Serious Unexpected Adverse Events

An SAE is any untoward medical occurrence that at any dose

- Results in death,
- Is life-threatening (at the time of the event),
- Requires inpatient hospitalization or prolongation of existing hospitalization,
- Results in persistent or significant disability/incapacity, or
- Is a congenital anomaly/birth defect.

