9.3 Adverse Event Reporting Procedures

9.3.1 Reporting Adverse Events

All AEs, including overdose with sequelae or intentional overdose of study drug or other medication, must be recorded on the appropriate AE reporting page of the subject's AE log whether or not they are considered causally related to study drug.

For every AE, the Investigator must:

9.3.1.1 Provide an assessment of the seriousness of the event (ie, is it an SAE?), as well as the severity and causal relationship to the study drug.

9.3.1.2 Document all actions taken with regard to study drug;

9.3.1.3 Detail any other treatment measures taken for the AE.

Any AEs that are ongoing at the time of the End of study visit will be followed until the condition returns to pre-study status, has resolved, or stabilized, or can be explained as being unrelated to study drug. If a follow-up visit is deemed necessary for appropriate safety surveillance, it will take place within 30 days of the last known dose of study drug.

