9.3.2 Reporting Serious Adverse Events

The Investigator will inform the Sponsor (ITI) and regulatory authorities of SAEs that meet specific criteria. Therefore, the Sponsor must be notified immediately regarding any SAE that occurs after informed consent is obtained.

Within 24 hours of learning of any AE that meets one of the criteria for an SAE, the study center personnel must report the event to the Sponsor on the SAE Report Form.

If, during follow-up, any nonserious AE worsens and eventually meets the criteria for an SAE, that AE should be recorded as a new SAE.

Table 2. describes the Classification of Adverse Event Causality and **Table 3.** Outlines the Outcomes of AEs or SAEs

Table2.

Classification	Definition
Unrelated	The AE or SAE is judged to be clearly and incontrovertibly due only to extraneous causes (e.g., disease, environment) and does not meet the criteria for study drug relationship listed under probable, possible, or unlikely.
Unlikely	The AE or SAE is unlikely related to the study drug, when the AE or SAE: 
• Does not follow a reasonable temporal sequence from administration of the study drug.• May readily have been produced by the subject's clinical state, environmental or toxic factors, or other modes of therapy administered to the subject.• Does not follow a known pattern of response to the study drug.• Does not reappear or worsen when the study drug is re-administered.
Possible	The AE or SAE is possibly related to the study drug when the connection to the study drug appears unlikely but cannot be ruled out with certainty. This causal relationship is assigned when the AE or SAE: 
• Follows a reasonable temporal sequence from administration of the study drug.• May have been produced by the subject's clinical state, environmental or toxic factors, or other modes of therapy administered to the subject.

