The PI and DSMB will be ultimately responsible for monitoring the safety and efficacy of the trial, executing the DSM plan, and complying with reporting requirements. Any adverse events (AE) that occur will be monitored in an ongoing way, as well as being formally reviewed by the investigators and at each annual review meeting. Any data accrued will be summarized and reviewed by the study investigators at each annual review meeting and after 50% of participants have been enrolled. Interim analyses will not be performed unless clinically indicated. All SAEs, such as death, hospitalization, will be reported to the IRB, FDA, and the sponsor under expedited reporting in accordance with policy. The procedures for this reporting include written documentation using the clinical notes related to the adverse event and specific forms detailing the event with a sign-off by all appropriate supervisory personnel. We will report major protocol amendments or changes in the informed consent to the sponsor, as well as any temporary or permanent suspension of patient accrual.

The board will include [name], University of Wisconsin Madison, [name], Yale University, and [name], Yale University

43c. Describe any pre-specified safety threshold or criteria that would trigger immediate suspension of the study, if applicable.

It would depend on the evaluation of serious adverse events.

Privacy & Confidentiality

44. Participant Privacy

Privacy refers to an individual's right to control how others view, record, or obtain information about them. Privacy protections apply to people, while confidentiality protections (addressed in the next item), apply to data.

In this section, describe how the study team will protect participants' privacy throughout all phases of the research, including during identification, recruitment, screening, the consent process, the conduct of the study, and dissemination of data. For example, consider the locations where you will approach and question participants, the locations where data will be viewed/analyzed, how data collection procedures will limit the amount of sensitive or invasive data collected to only what is necessary to answer the research questions, how participants will be described in publications/presentations, etc.

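### The SAE definition in section 9.2 has no medical-judgement criterion, so suicidal behaviour or an intentional overdose that meets none of its five outcomes is not reported on an expedited basis

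*Protocol*

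**What the plan says.** Section 9.2 of the protocol begins its definition with "An SAE is any untoward medical occurrence that at any dose" and lists five outcomes. After death come:

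- a threat to life, worded as "Is life-threatening (at the time of the event");
- an admission criterion, worded as "Requires inpatient hospitalization or prolongation of existing hospitalization";
- lasting disability;
- birth defect, which closes the list.

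Three other provisions depend on that definition.

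- Section 9.3.2 sets the sponsor report: "Within 24 hours of learning of any AE that meets one of the criteria for an SAE", site staff must send the SAE form.
- Item 43b applies expedited reporting to the IRB, the FDA and the sponsor to SAEs.
- Item 43c asks for any pre-specified criteria for immediate suspension of the study and answers: "It would depend on the evaluation of serious adverse events".

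Section 9.3.1 governs what is logged. It covers "All AEs, including overdose with sequelae or intentional overdose of study drug or other medication", and asks the investigator to rate seriousness, severity and causality for each event. Section 7.5 has the C-SSRS completed at every visit, and item 43a lists it among the safety data to be monitored.

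**The concern.** The participants have major depression with a MADRS total of at least 22 and an inadequate response to their current antidepressant. Criterion 2 in section 2.2 screens out recent suicidal ideation on C-SSRS items 4 or 5, attempts within one year, and scores of 4 or more on MADRS item 10. Those sub-items do not exclude attempts more than a year old or lower item 10 scores, although the investigator may still exclude on overall judgement. The plan then looks for suicidal behaviour at every visit and names intentional overdose as an event to be logged.

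Having provided for detection, the protocol gives these events no fast reporting route unless they meet one of the five outcomes. At stake is how quickly the sponsor, the IRB and the FDA hear of a suicide attempt or intentional overdose that did not lead to admission.

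**Working it through.** No arithmetic applies, and the plan states no figure on this point. The check is to follow one type of event through the protocol's own rules.

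**The event.** A participant makes a suicide attempt or takes an intentional overdose. It is not life-threatening at the time, is treated without inpatient admission and leaves no lasting disability.

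**Step 1: is the list closed?** The fourth criterion ends with the conjunction that introduces the last one: "Results in persistent or significant disability/incapacity, or" is followed only by "Is a congenital anomaly/birth defect". Nothing after it extends the list, and no item turns on medical judgement.

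**Step 2: compare the event with each criterion.**

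| Criterion in section 9.2 | Met? |
|---|---|
| Death | No |
| Life-threatening at the time | No |
| Inpatient admission or longer stay | No |
| Lasting or significant disability | No |
| Birth defect | No |

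The event meets 0 of 5, so it is nonserious.

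**Step 3: does the seriousness rating in section 9.3.1 rescue it?** No. That section equates seriousness with being an SAE and offers no other standard, so the rating returns to the same five items.

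**Step 4: follow the consequences.**

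| Provision | Depends on SAE status? | Applies to this event? |
|---|---|---|
| Adverse event log (9.3.1) | No | Yes |
| C-SSRS at each visit (7.5) | No | Yes |
| Ongoing monitoring and formal review of adverse events (43b) | No | Yes |
| 24-hour sponsor report (9.3.2) | Yes | No |
| Expedited report to IRB, FDA and sponsor (43b) | Yes | No |
| Evaluation named in the suspension answer (43c) | Yes | No |

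**Step 5: how soon would formal review see it?** Item 43b schedules formal adverse event review at annual meetings, and a review of accrued data then and after 50% enrolment, which is 0.5 × 50 = 25 participants. One participant's course lasts 2 + 6 + 1 = 9 weeks. A participant can therefore start and finish between formal reviews. The ongoing monitoring in the same item may act sooner, but it has no stated interval.

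**The case against.** There are four serious points on the other side.

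- **The events are not lost.** A reader might infer that suicidal behaviour goes uncounted. The documents do not support that: the log, the C-SSRS and the adverse event review all hold it. This objection stands, and the point is confined to classification and speed of reporting.
- **Many attempts already qualify.** A reader might infer that every attempt managed without admission is left out. It is not: one that was life-threatening at the time, or that left significant disability, is an SAE wherever it was treated. Section 9.3.2 also requires a nonserious event that later worsens to meet a criterion to be recorded as a new SAE. This stands too, and it narrows the gap.
- **Item 43c is not a fixed trigger.** A reader might infer that such events slip past the one rule that would halt the trial. The answer there is discretionary and carries no threshold. Item 43b makes the PI and the DSMB responsible for safety without limiting them to SAEs, and it mentions suspension of accrual without tying that to SAE status. What remains is that the evaluation named in 43c concerns SAEs, and this event is not one.
- **Other papers may fill the gap.** Section 9 refers to site SOPs, and the sponsor's SAE form and any monitoring charter are not shown. They might widen reporting in practice. However, section 9 cites the SOPs for managing events, while the definition itself is fixed in section 9.2.

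It is also true that no passage contradicts section 9.2. The point rests on what follows when that list is applied as written.

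**Conclusion.** The concern holds in this limited form. Under the protocol as written, suicidal behaviour or an intentional overdose that is not life-threatening at the time, not admitted and not disabling is a nonserious event, and it falls outside the three provisions that depend on SAE status.

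Its size cannot be estimated, because the documents give no expected frequency for such events. Expressing it as a change in an arm's SAE rate would not help either, since section 11 specifies no comparison of SAE rates and none of the five aims in item 4 is a safety aim. The primary efficacy analysis is not affected.

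The conclusion assumes that staff apply section 9.2 literally and that no unseen document overrides its definition. It is a modest weakness in the safety rules, worth correcting because the correction is cheap.

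**What to change.** Add a sixth bullet to section 9.2, moving the closing conjunction accordingly: 'Is an important medical event that, in the investigator's judgement, may jeopardise the subject or require intervention to prevent one of the above outcomes (for example, a suicide attempt or intentional overdose).'

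Section 9.3.2 and items 43b and 43c need no rewording, because each relies on SAE status and picks up the wider definition. The SAE form and site SOPs should be checked for agreement with the new text. The cost is one sentence and a few more expedited reports in a trial of 50 participants. The change concerns classification and reporting only and alters no treatment rule.

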9.3 Adverse Event Reporting Procedures

9.3.1 Reporting Adverse Events

All AEs, including overdose with sequelae or intentional overdose of study drug or other medication, must be recorded on the appropriate AE reporting page of the subject's AE log whether or not they are considered causally related to study drug.

For every AE, the Investigator must:

9.3.1.1 Provide an assessment of the seriousness of the event (ie, is it an SAE?), as well as the severity and causal relationship to the study drug.

9.3.1.2 Document all actions taken with regard to study drug;

9.3.1.3 Detail any other treatment measures taken for the AE.

Any AEs that are ongoing at the time of the End of study visit will be followed until the condition returns to pre-study status, has resolved, or stabilized, or can be explained as being unrelated to study drug. If a follow-up visit is deemed necessary for appropriate safety surveillance, it will take place within 30 days of the last known dose of study drug.

9.3.2 Reporting Serious Adverse Events

The Investigator will inform the Sponsor (ITI) and regulatory authorities of SAEs that meet specific criteria. Therefore, the Sponsor must be notified immediately regarding any SAE that occurs after informed consent is obtained.

Within 24 hours of learning of any AE that meets one of the criteria for an SAE, the study center personnel must report the event to the Sponsor on the SAE Report Form.

If, during follow-up, any nonserious AE worsens and eventually meets the criteria for an SAE, that AE should be recorded as a new SAE.

Table 2. describes the Classification of Adverse Event Causality and **Table 3.** Outlines the Outcomes of AEs or SAEs

Table2.

Classification	Definition
Unrelated	The AE or SAE is judged to be clearly and incontrovertibly due only to extraneous causes (e.g., disease, environment) and does not meet the criteria for study drug relationship listed under probable, possible, or unlikely.
Unlikely	The AE or SAE is unlikely related to the study drug, when the AE or SAE: 
• Does not follow a reasonable temporal sequence from administration of the study drug.• May readily have been produced by the subject's clinical state, environmental or toxic factors, or other modes of therapy administered to the subject.• Does not follow a known pattern of response to the study drug.• Does not reappear or worsen when the study drug is re-administered.
Possible	The AE or SAE is possibly related to the study drug when the connection to the study drug appears unlikely but cannot be ruled out with certainty. This causal relationship is assigned when the AE or SAE: 
• Follows a reasonable temporal sequence from administration of the study drug.• May have been produced by the subject's clinical state, environmental or toxic factors, or other modes of therapy administered to the subject.

Probable	
The AE or SAE is probably related to the study drug when the connection to study drug can be made with a high degree of certainty. This causal relationship is assigned when the AE or SAE:
 
 Follows a reasonable temporal sequence from administration of the study drug. Cannot be reasonably explained by the known characteristics of the subject's clinical state, environmental or toxic factors, or other modes of therapy administered to the subject. Disappears or decreases upon cessation or reduction in dose (note that there are important exceptions when an AE or SAE does not disappear upon discontinuation of the study drug, yet drug relatedness clearly exists e.g., bone marrow depression or tardive dyskinesia). Follows a known pattern of response to the suspected study drug.
Definite	
The AE or SAE is definitely related to the study drug when the event:
 
 Follows a reasonable temporal sequence from administration of the study drug. Follows a known pattern of response to the suspected study drug. Is confirmed by improvement on stopping and reappearance of the event on repeated exposure to the study drug. Cannot be reasonably explained by the known characteristics of the subject's clinical state.

Table 3.

Classification	Definition
Fatal	The study subject died.
Resolved	The AE or SAE has ended.
Resolved with Sequelae	The AE or SAE has ended but changes are noted from Baseline.
Unresolved	
The AE has not ended.
 
An AE outcome can only be categorized as unresolved if the AE is:
 
 Ongoing at the end of the reporting period (i.e., 30 days after the last dose of study drug), and the Investigator deems that further follow-up is not medically required. Lost to follow-up after repeated unsuccessful attempts to contact the subject. Ongoing and referred to the subject's physician or a specialist for follow-up.

Reporting Procedure:

SAE Reporting E-mail: [contact]

SAE Reporting [contact]

Medical Emergency Contact numbers:

Americas (North and South America)/APAC

[contact] (Primary)

[contact] (Alternate)

10. Neuroimaging procedures.

Whole brain fMRI will be acquired using a 3T Siemens Vida MRI scanner with a 64-channel head coil at the Biomedical Imaging Center at the University of Texas at Austin. A high-resolution T1-weighted structural volume (256x256x192, 1-mm³ resolution) will be acquired for coregistration and normalization. Functional images will be collected using an adapted version of the ABCD project protocol used in our Biomedical Imaging Center, enabling both high temporal (TR=786ms) and spatial (2.4mm isotropic voxels) resolution, using a 32 channel head coil. We use fMRIPREP to preprocess the data. Standard preprocessing steps will occur prior to within-subject and between-subject analyses.

Approach-Avoidance Learning Task. Participants are instructed to learn, through trial-and-error, which of three responses, indicated with distinct stimuli, to select to achieve a particular outcome. Critically, each response option is associated with a probability of *both* a reward outcome (points) *and* an aversive outcome (i.e., a mild electric shock). Consistent with reinforcement tasks, the response-outcome contingencies (e.g., which option is most likely to lead to reward) switch throughout the task, such that half the time the option that is most likely to lead to reward is also most likely to lead to a shock, and half the time the highest reward option is least likely to lead to shock. Thus, the task systematically manipulates congruency and conflict between reward-threat outcomes and additionally introduces a reversal learning^{61,147} probe for both reward and threat. To motivate adherence to instructions, participants are told they will receive monetary compensation in proportion to how well they perform. In contrast to fear conditioning tasks that instruct participants to select a shock intensity that nears painful (7/10 Likert scale), we would have participants select a level that is annoying and mildly uncomfortable (5/10) to enable tolerance of repeated stimulations, as the number of shocks delivered could be higher than during standard conditioning tasks. There would be 150 trials of the task. Each initial cue is presented until the participant makes a selection, followed by a jittered anticipation phase (2-4s), and then the threat outcome (mild electric shock) and reward outcome (points) would be presented sequentially and separated by a jittered ITI of 3-6s. Given that outcomes are driven probabilistically following participant choices, the total number of shocks delivered can vary.

8. Data Analysis

Describe the data analysis plan, including any statistical procedures or power analysis.

11. Statistical Analysis

11.2 Statistical And Analytic Plan

The primary efficacy endpoint is the change from baseline to end of Week 6(EOT) in MADRS total score. Based on the primary hypothetical estimand strategy which assumes patients are on study drug up to the primary time point (end of Week 6), MADRS assessments collected off-treatment (ie, efficacy assessment performed more than 3 days after last dose of study drug) and/or after starting new treatment for MDD will be set to missing (except those collected for patients discontinued due to and will not be included in the primary analysis). The missing data in patients who discontinued due to lack of efficacy (LOE) or due to taking non-study treatment for MDD will be assumed missing-not-at-random. The missing data in patients who discontinued due to other reasons will be assumed as missing- at-random. Missing data will be imputed accordingly to recent recommendations using the ‘mice’ package in R.^{25,26}

The primary analysis will use a mixed-effects model for repeated measures (MMRM) to analyze the change from baseline to end of Week 6 in MADRS total score. Similar MMRM models will be used for secondary endpoints. An additional analysis will examine slopes of MADRS scores over the 6 week period, testing the hypothesis that the active drug group will have a steeper slope of MADRS over the 6 week period. Additional models will test for non-linear patterns of change as well. Similar analyses will be conducted on secondary outcomes (e.g. CGI, PTSD

symptom severity, etc.).

For imaging data, following standard preprocessing, beta coefficients of voxelwise brain activity will be defined using standard general linear models. These coefficients will be used in multivariate pattern analysis (MVPA) to build classifiers, using support vector machines (SVM), of reward and threat using leave-one-out cross-validation and quantify reward and threat anticipation during the task. MVPA classifier output will be analyzed using mixed effects models. Threat and reward anticipation as predictors of treatment outcome will be analyzed by including these variables as a predictor in the MMRM described above. Threat and reward anticipation as targets of treatment will be analyzed in mixed effects model with post-treatment classifier output as the dependent measure and including predictors of drug group and including pre-treatment classifier output as a covariate.

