2.4 Study Withdrawal or Removal from the Study

Patients can be prematurely discontinued from the study drug or the study for one of the following reasons:

- Death
- AE
- Lack of efficacy or insufficient therapeutic response
- Lost to follow-up
- Protocol violation
- Study terminated by Investigator
- Withdrawal of consent (by the patient)
- Pregnancy
- Other (such as site closure, administrative reasons, etc)

NOTE: If a patient discontinues due to withdrawal of consent and either a concurrent AE was reported or concurrent lack of efficacy was documented, the study staff will confirm the primary reason for discontinuation and record the primary reason for discontinuation in the subject binder (CRF).

Patients who discontinue from the study and do not return to the study site for final assessments must be requested in writing to return to the site for a final assessment. A copy of the letter, together with the source documentation, will be kept in the Investigator's files. The reason for premature discontinuation from the study will be recorded in the subject study binder.

3. Treatment

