3.7.1 Prohibited Medications

Use of the following products during the study is prohibited: any known 5-HT2A receptor antagonist or inverse agonist, any moderate or strong CYP3A4 inhibitor or any CYP3A4 inducer, or any drugs with known psychotropic properties other than those listed in [Section 6.7](#) or any non-psychotropic drugs with potential central nervous system effects.

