11.3 Primary Endpoint Estimand

The primary efficacy endpoint is the absolute change in MADRS total scores from Baseline to end of Treatment visit at Week 6 in subjects on ADT plus Lumateperone or matching placebo.

The main estimand for the primary efficacy endpoint is defined as follows:

- Target population(TP):Total Population: All randomized participants with MDD and history of early life abuse (Baseline MADRS score ≥ 22) as defined by the study inclusion/exclusion criteria who are randomized and dosed

- Variable: Change from Baseline to Week 6 in the MADRS total scores (Visit 7)

Intercurrent events (ICE)

1. Study or treatment discontinuation

- a. Due to lack of efficacy

- b. Due to adverse event related to study medication

- c. Due to adverse event unrelated to study medication

- d. Due to other reasons

2. Treatment with prohibited medication

3. Death

- a. Related to MDD

- b. Unrelated to MDD

- ICE strategy

- o ICE 1a, 1b, 2: A hypothetical strategy will be applied assuming that patients after the ICE follow the course of patients receiving placebo.

- o ICE 1c, 1d, 3b: A hypothetical strategy will be applied assuming that patients after the ICE follow the course of the arm they were randomized to.

- o ICE 3a: A composite strategy will be applied by imputing values after the ICE with the worst possible MADRS score (=60).

10.2 Secondary Endpoint Estimand: The key secondary efficacy endpoint is the change from baseline to end of Week 6 in the CGI-S score.

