11.4 Efficacy Estimand Analysis

Main estimands are defined for the primary efficacy variable:

- Absolute change from Baseline to Week 6 of the MADRS total score

and for the following 3 key secondary efficacy variables in hierarchical rank order of the hypothesis testing procedure:

- MADRS response rate (proportion of subjects with an improvement $\geq 50\%$ in the Baseline MADRS total score) at End of Treatment (EOT) Week 6, Lumateperone as compared to placebo

- MADRS remission rate (proportion of subjects with a MADRS total score ≤ 10) EOT Week 6, Lumateperone as compared to placebo

- Change from Baseline to EOT Week -6 in the Clinical Global Impression of Severity (CGI-S) score, Lumateperone as compared to placebo

Confirmatory testing will be performed only for these main estimands, whereby the testing of the key secondary estimands will follow the ordered hierarchical approach.

The primary statistical analysis of all confirmatory tested estimands will be performed on the Total Population, using the mixed-effect model repeated measure (MMRM) analysis. For the main primary estimand, the changes from baseline in MADRS total score will be analyzed using a Mixed Model with

Repeated Measures (MMRM). This model will include Treatment, Visit, Treatment-by-Visit interaction and the number of failed prior treatments (1 or more than 1) as fixed effects, Baseline value as a covariate, and Visit as the repeated effect. The estimated means for each arm as well as the estimated treatment effect (Lumateperone – Placebo) along with the 95% confidence intervals for the treatment effect will be presented for each visit. The primary estimand will be estimated as the difference between treatment means (MMRM least-squares) at the EOT Week 6 (Visit 7).

As a sensitivity analysis for all estimands, the MMRM analysis will be performed using a range of missing value imputations. For the main estimand of the primary efficacy, a tipping point analysis will be applied to investigate the robustness of the analysis results.

Study Elements Requiring Additional Information or Approvals

9. Public Registration and Reporting Requirements

Federal regulations, policy, and some journal guidelines require public registration and results reporting for studies that meet the definition of a clinical trial.

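### The primary missing-data rules in Section 11.2 do not match the Section 11.3 estimand that Section 11.4 tests

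*Protocol*

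**What the plan says.** Section 11.2 bases the primary analysis on a "primary hypothetical estimand strategy which assumes patients are on study drug up to the primary time point (end of Week 6"). It discards MADRS scores taken more than 3 days after the last dose, or "after starting new treatment for MDD will be set to missing". It then sorts missing data into two classes. Dropout for lack of efficacy or for non-study MDD treatment is missing not at random. All other dropout falls in a residual class: "The missing data in patients who discontinued due to other reasons will be assumed as missing- at-random".

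Section 11.3 defines the main estimand for the same endpoint through a list of intercurrent events (ICEs) with three rules:

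- Lack of efficacy (1a), drug-related adverse event (1b) and prohibited medication (2): "ICE 1a, 1b, 2: A hypothetical strategy will be applied assuming that patients after the ICE follow the course of patients receiving placebo".
- Unrelated adverse event (1c), other reasons (1d) and death unrelated to MDD (3b): the course of the randomised arm.
- MDD-related death (3a): "ICE 3a: A composite strategy will be applied by imputing values after the ICE with the worst possible MADRS score (=60").

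Section 11.4 says "Confirmatory testing will be performed only for these main estimands" and names an MMRM. It does not say which of the two sets of rules prepares the data for that model.

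**The concern.** Both sections set rules for one primary endpoint, and each presents its own rules as the main or primary ones. If they differ for an event that can occur, two analysts who each follow the protocol can report different primary estimates. An analyst who applies 11.2 does not estimate the quantity that 11.4 reserves for confirmatory testing.

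If the choice is left open, it could also be made after unblinding. For drug-related dropout the choice is not neutral: if lumateperone works, the 11.2 rule is expected to give the larger effect.

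**Working it through.** **Step 1. Compare the two sections event by event.** Section 2.4 matters here. It opens its list with "Patients can be prematurely discontinued from the study drug or the study for one of the following reasons", and the list includes death and adverse events, so both can enter the residual class of 11.2. Section 3.7.1 matters for ICE 2, because prohibited products include "any moderate or strong CYP3A4 inhibitor or any CYP3A4 inducer, or any drugs with known psychotropic properties", which is wider than treatment for MDD.

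| Event | Section 11.2 | Section 11.3 | Agree? |
|---|---|---|---|
| 1a, lack of efficacy | Not at random, model not named | Placebo course | Compatible |
| 1b, drug-related adverse event | At random | Placebo course | **No** |
| 1c and 1d | At random | Randomised arm | Yes |
| 2, treatment for MDD | Scores set to missing; not at random | Placebo course | Compatible |
| 2, other prohibited drug, stays on study drug | Observed scores kept | Placebo course | **No** |
| 2, other prohibited drug, study drug stopped | At random | Placebo course | **No** |
| 3a, MDD-related death | At random | MADRS 60 | **No** |
| 3b, unrelated death | At random | Randomised arm | Yes |

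The premise in 11.2 that patients are on study drug to Week 6 also does not describe a placebo course for 1a, 1b and 2.

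**Step 2. Inputs for size.** The protocol gives 25 patients per arm. It gives no effect, SD or dropout rate, so there is no figure of its own to reproduce. Assumed: SD 9, effect Δ of 3 to 5 MADRS points, Week 6 arm mean of 15 to 25.

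SE of the difference = 9 × √(2/25) = 2.55.

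**Step 3. ICE 1b.** Suppose k lumateperone patients move from their own arm's course to the full placebo course. The gap is (k/25) × Δ.

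| k | Δ = 3 | Δ = 5 |
|---|---|---|
| 1 | 0.12 | 0.20 |
| 2 | 0.24 | 0.40 |
| 3 | 0.36 | 0.60 |

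In standard errors the range is 0.12/2.55 = 0.05 to 0.60/2.55 = 0.24. In the placebo arm the two rules coincide. The 11.3 effect is the smaller one in expectation only if the drug works.

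**Step 4. ICE 2, drug not given for MDD, one patient in 25.**

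- A lumateperone patient who keeps, or is imputed, the full benefit under 11.2 makes the 11.3 effect smaller by 3/25 to 5/25 = 0.12 to 0.20 points.
- A placebo patient who stays in with an assumed gain of 3 to 5 points from the prohibited drug makes the 11.3 effect larger by the same amount.
- A placebo patient who is stopped gives no gap.

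The direction is therefore unknown.

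**Step 5. ICE 3a, one patient in 25.** The arm mean moves by (60 − m)/25, where m is the Week 6 arm mean.

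- m = 25: 1.40 points (0.55 SE)
- m = 20: 1.60 points (0.63 SE)
- m = 15: 1.80 points (0.71 SE)

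The sign depends on the arm. On the change scale the imputed change is 60 minus baseline. With baselines of 22 to 40 and an assumed missing-at-random change of −8 to −16, the shift ranges from (20 + 8)/25 = 1.12 to (38 + 16)/25 = 2.16 points.

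**The case against.** The strongest reply is that only ICE 1b is a plain contradiction. Section 11.2 does not mention death, and 11.3 keeps death apart from discontinuation, so 11.3 may simply fill a gap. Likewise 11.2 may be silent, not contrary, on prohibited drugs not given for MDD. Neither reading removes the conflict. Section 2.4 lists death among the reasons for discontinuation, so the residual rule covers it. Section 11.2 also says which scores are removed, so scores after other prohibited drugs stay in.

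Four further points deserve weight:

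- One clause in 11.2, an exception for certain discontinued patients, is broken in the text available and its reason is missing. If it named adverse events, their off-treatment scores would be kept, and the 1b gap would have a different form and size. It would still not be the placebo course.
- Missing not at random can be implemented as a placebo course, so 1a and treatment for MDD are compatible. That is accepted in the table.
- The sizes are small and assumed. Step 3 takes the whole benefit as lost, and partial carry-over would give less. The placebo-arm gain in Step 4 has no support in the protocol and is unlikely for a CYP3A4 drug in a patient not taking lumateperone.
- Section 11.4 plans a range of imputations and a tipping-point analysis. These show robustness, but they do not say which estimate is primary.

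That a SAP may exist does not answer the point. The protocol already fixes both rules, and a SAP that follows one departs from the other.

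**Conclusion.** The concern holds and should be fixed. Sections 11.2 and 11.3 give different rules for drug-related adverse event dropout, for prohibited medication not given for MDD and for MDD-related death. They agree on 1c, 1d and 3b and are compatible on 1a and on treatment for MDD.

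The most likely practical source of difference is ICE 1b. Its expected size is modest, 0.05 to 0.24 of a standard error for one to three lumateperone patients under the assumptions above. An MDD-related death has a large effect per event but is unlikely in 50 patients screened for suicide risk. The inconsistency itself follows from the text and does not depend on any assumed figure.

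**What to change.** State in 11.2 that the 11.3 main estimand governs the primary analysis, and apply its ICE list in both arms:

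- 1a, 1b and 2: impute from the placebo-arm course, for example by reference-based multiple imputation.
- 1c, 1d and 3b: impute at random within the randomised arm.
- 3a: set to 60.

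Keep the 3-day window as the operational definition of when scores after treatment discontinuation begin. Delete the premise that patients are on study drug to Week 6, and complete the broken exception clause so that it agrees with the list. Label any on-drug, missing-at-random analysis as supplementary for a different estimand. If the authors prefer the 11.2 rules, 11.3 must be rewritten to match. Either change must be made before unblinding.

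The cost is wording, a little imputation code and, if 11.3 governs, the loss of observed scores after prohibited medication. For 1b the expected estimate becomes slightly smaller if the drug works; for ICE 2 the direction is unknown. Visits, procedures and sample size do not change.
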